#### **6.4.1.2 Nausea/vomiting**

Nausea and vomiting should be treated aggressively, and consideration should be given in subsequent cycles to the administration of prophylactic antiemetic therapy according to standard institutional practice. Patients should be strongly encouraged to maintain liberal oral fluid intake.

#### **6.4.1.3 Infection**

Patients with a documented infectious complication should receive oral or i.v. antibiotics or other anti-infective agents as considered appropriate by the treating investigator for a given infectious condition, according to standard institutional practice.

#### **6.4.1.4 Immune-related adverse events**

Please see Section 7.5 below and the separate guidance document in the administrative binder regarding diagnosis and management of adverse experiences of a potential immunologic aetiology.

#### **6.4.1.5 Management of Infusion Reactions**

Acute infusion reactions (which can include cytokine release syndrome, angioedema, or anaphylaxis) are different from allergic/hypersensitive reactions, although some of the manifestations are common to both AEs. Signs and symptoms usually develop during or shortly after drug infusion and generally resolve completely within 24 hours of completion of infusion. Signs/symptoms may include: Allergic reaction/hypersensitivity (including drug fever); Arthralgia (joint pain); Bronchospasm; Cough; Dizziness; Dyspnoea (shortness of breath); Fatigue (asthenia, lethargy, malaise); Headache; Hypertension; Hypotension; Myalgia (muscle pain); Nausea; Pruritus/itching; Rash/desquamation; Rigors/chills; Sweating (diaphoresis); Tachycardia; Tumour pain (onset or exacerbation of tumour pain due to treatment); Urticaria (hives, welts, wheals); Vomiting. Table 9 below shows treatment guidelines for patients who experience an infusion reaction associated with administration of pembrolizumab.

### **6.5 Supportive Care Guidelines for Immune-related Adverse Events (irAE) and Immune-related Events of Clinical Interest (irECI)**

Immune-related Adverse Events (irAEs) may be defined as an AE of unknown etiology, associated with drug exposure and is consistent with an immune phenomenon. irAEs may be predicted based on the nature of the pembrolizumab compound, its mechanism of action, and reported experience with immunotherapies

that have a similar mechanism of action. Special attention should be paid to AEs that may be suggestive of potential irAEs. An irAE can occur shortly after the first dose or several months after the last dose of treatment. If an irAE is suspected, efforts should be made to rule out cancer, infectious, metabolic, toxin or other etiologic causes prior to labelling an AE as an irAE. Patients who develop a Grade 2 or higher irAE should be discussed immediately with the Chief Investigator or delegate.

Recommendations to managing irAEs not detailed elsewhere in the protocol are detailed in Table 10.

**Table 9:** Infusion Reaction Treatment Guidelines

NCI CTCAE Grade	Treatment	Premedication at subsequent dosing
Grade 1 Mild reaction; infusion interruption not indicated; intervention not indicated	Increase monitoring of vital signs as medically indicated until the patient is deemed medically stable in the opinion of the investigator.	None
Grade 2 Requires infusion interruption but responds promptly to symptomatic treatment (e.g., antihistamines, NSAIDS, narcotics, IV fluids); prophylactic medications indicated for < =24 hrs	
Stop Infusion and monitor symptoms. Additional appropriate medical therapy may include but is not limited to:
 
 
IV fluids
 
Antihistamines
 
NSAIDS
 
Paracetamol
 
Narcotics
 
 
Increase monitoring of vital signs as medically indicated until the patient is deemed medically stable in the opinion of the investigator. If symptoms resolve within one hour of stopping drug infusion, the infusion may be restarted at 50% of the original infusion rate (e.g. from 100 mL/hr to 50 mL/hr). Otherwise dosing will be held until symptoms resolve and the patient should be pre-medicated for the next scheduled dose.
 
Patients who develop Grade 2 toxicity despite adequate premedication should be permanently discontinued from further trial treatment administration.
	Patient may be pre-medicated 1.5h ( $\pm$ 30 minutes) prior to infusion of pembrolizumab with:  Diphenhydramine 50 mg po (or equivalent dose of antihistamine).  Paracetamol 500-1000 mg po (or equivalent dose of antipyretic).
Grades 3 or 4 Grade 3: Prolonged (i.e., not rapidly responsive to symptomatic medication and/or brief interruption of infusion); recurrence of symptoms following initial improvement; hospitalization indicated for other clinical sequelae (e.g., renal impairment, pulmonary infiltrates)  Grade 4: Life-threatening; Pressor or ventilator support indicated	
Stop Infusion. Additional appropriate medical therapy may include but is not limited to:
 
 
IV fluids
 
Antihistamines
 
NSAIDS
 
Paracetamol
 
Narcotics
 
Oxygen
 
Pressors
 
Corticosteroids
 
Epinephrine
 
 
Increase monitoring of vital signs as medically indicated until the patient is deemed medically stable in the opinion of the investigator. Hospitalization may be indicated.
 
Patient is permanently discontinued from further trial treatment administration.
	No subsequent dosing

Appropriate resuscitation equipment should be available in the room and a physician readily available during the period of drug administration.
 
For Further information, please refer to the Common Terminology Criteria for Adverse Events version 4.0 (CTCAE) at http://ctep.cancer.gov
		

**Table 10:** General Approach to Handling irAEs

irAE	Withhold/Discontinue Pembrolizumab?	Supportive Care
Grade 1	No action	Provide symptomatic treatment
Grade 2	May withhold pembrolizumab. For recurrent grade 2 pneumonitis, pembrolizumab should be discontinued permanently.	Consider systemic corticosteroids in addition to appropriate symptomatic treatment. Steroid taper should be considered once symptoms improve to Grade 1 or less and tapered over at least 4 weeks. Based on limited data from clinical studies in subjects whose immune-related adverse reactions could not be controlled with corticosteroid use, administration of other systemic immunosuppressants can be considered.
Grade 3 and Grade 4	Withhold pembrolizumab Discontinue if unable to reduce corticosteroid dose to < 10 mg per day prednisone equivalent within 12 weeks of toxicity	Systemic corticosteroids are indicated in addition to appropriate symptomatic treatment. May utilize 1 to 2 mg/kg prednisone or equivalent per day. Steroid taper should be considered once symptoms improve to Grade 1 or less and tapered over at least 4 weeks. Based on limited data from clinical studies in subjects whose immune-related adverse reactions could not be controlled with corticosteroid use, administration of other systemic immunosuppressants can be considered.
Please Note: If an irAE does not resolve or improve to ≤ Grade 1 within 12 weeks after last administration of pembrolizumab, study therapy discontinuation should be considered after discussion with a Merck Clinical Director via the RM-CTU trial manager.		

Details for managing specific irAEs are summarised below:

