### 6.2.9.2 Dose Modification

Pembrolizumab will be withheld for drug-related Grade 4 haematological toxicities, and non-haematological toxicity  $\geq$  Grade 3 including laboratory abnormalities, and severe or life-threatening AEs as per Table 8 below.

In case toxicity does not resolve to Grade 0-1 within 12 weeks after last infusion, trial treatment should be discontinued after consultation with the Sponsor. With Investigator and Sponsor agreement, patients with a laboratory AE still at Grade 2 after 12 weeks may continue treatment in the trial only if asymptomatic and controlled. For information on the management of AEs, see Section 7 and Table 8. Patients who experience a recurrence of the same severe or life-threatening event at the same grade or greater with re-challenge of pembrolizumab should be discontinued from trial treatment.

Events of Clinical interest (ECI) can be potential irAEs and dose modifications for these toxicities should they occur can be found in Appendix 5 and as per the MSD guidance document for pembrolizumab ECI version 3.0.

Dosing interruptions are permitted in the case of medical / surgical events or logistical reasons not related to study therapy (e.g., elective surgery, unrelated medical events, patient vacation, and/or holidays). Subjects should be placed back on study therapy within 3 weeks of the scheduled interruption, unless otherwise discussed with the Sponsor. The reason for interruption should be documented in the patient's study record.

**Table 8:** Dose modification guidelines for drug-related adverse events.

Toxicity	Hold Treatment For Grade	Timing for Restarting Treatment	Treatment Discontinuation
Diarrhoea/Colitis	2-3	Toxicity resolves to Grade 0-1.	Toxicity does not resolve within 12 weeks of last dose or inability to reduce corticosteroid to 10 mg or less of prednisone or equivalent per day within 12 weeks.
	4	Permanently discontinue	Permanently discontinue
AST, ALT, or Increased Bilirubin	2	Toxicity resolves to Grade 0-1	Toxicity does not resolve within 12 weeks of last dose.
	3-4	Permanently discontinue (see exception below) 	Permanently discontinue
Type 1 diabetes mellitus (if new onset) or Hyperglycemia	T1DM or 3-4	Hold pembrolizumab for new onset Type 1 diabetes mellitus or Grade 3-4 hyperglycemia associated with evidence of beta cell failure.	Resume pembrolizumab when patients are clinically and metabolically stable.

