Hypophysitis	2-4	Toxicity resolves to Grade 0-1. Therapy with pembrolizumab can be continued while endocrine replacement therapy is instituted	Toxicity does not resolve within 12 weeks of last dose or inability to reduce corticosteroid to 10 mg or less of prednisone or equivalent per day within 12 weeks.
Hyperthyroidism	3	Toxicity resolves to Grade 0-1	Toxicity does not resolve within 12 weeks of last dose or inability to reduce corticosteroid to 10 mg or less of prednisone or equivalent per day within 12 weeks.
	4	Permanently discontinue	Permanently discontinue
Hypothyroidism		Therapy with pembrolizumab can be continued while thyroid replacement therapy is instituted	Therapy with pembrolizumab can be continued while thyroid replacement therapy is instituted.
Infusion Reaction	3-4	Permanently discontinue	Permanently discontinue
Pneumonitis	2	Toxicity resolves to Grade 0-1. If recurrent Grade 2 pneumonitis occurs pembrolizumab should be permanently discontinued.	Toxicity does not resolve within 12 weeks of last dose or inability to reduce corticosteroid to 10 mg or less of prednisone or equivalent per day within 12 weeks.
	3-4	Permanently discontinue	Permanently discontinue
Renal Failure or Nephritis	2	Toxicity resolves to Grade 0-1	Toxicity does not resolve within 12 weeks of last dose or inability to reduce corticosteroid to 10 mg or less of prednisone or equivalent per day within 12 weeks.
	3-4	Permanently discontinue	Permanently discontinue
All Other Drug-Related Toxicity 	3 or Severe	Toxicity resolves to Grade 0-1	Toxicity does not resolve within 12 weeks of last dose or inability to reduce corticosteroid to 10 mg or less of prednisone or equivalent per day within 12 weeks.
	4	Permanently discontinue	Permanently discontinue

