#### *Other immune-related AEs*

The following additional clinically significant, immune-mediated adverse reactions were reported in less than 1% (unless otherwise indicated) of subjects treated with pembrolizumab: uveitis, myositis, Guillain-Barré syndrome, pancreatitis and severe skin reactions (1.1%).

In addition a set of irAEs have also been classified as immune-related events of clinical interest (irECI) a full list of these can be found in events of clinical interest guidance and Appendix 5. Patients with symptomatic irECIs should immediately stop receiving pembrolizumab and be evaluated to rule out non treatment related causes of the event. Overdose and liver toxicity irECIs irrespective of relationship to the study drug should be reported within 24 hours of the investigator being aware to the Sponsor (via RM-CTU) who will in turn notify MSD. If the irECI is determined to be associated please refer to ECI guidance document and Appendix 5 for the recommendations on the management of these irECIs. If the event is not considered to be associated with the study drug the physician should exercise individual clinical judgment on the event management based on the patient. Any additional questions of the collection or information on management of irECIs should be directed to the Sponsor (via RM-CTU).

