
Other:
 
 
• Myocarditis¶
 
• Pericarditis
 
• Pancreatitis
 
• Any additional Grade 3 or higher event which the physician considers to be immune related
 
 
¶ Ensure that other causes of myocarditis are adequately evaluated to exclude other aetiologies
	Grade 2 or Grade 1 that do not improve with symptomatic treatment.	
 
• Report overdose and liver toxicity ECIs within 24 hours
 
• Withhold Pembrolizumab
 
• Consider biopsy for confirmation of diagnosis.
 
	
 
• Systemic corticosteroids may be indicated.
 
• If so:
 
• Treat with systemic corticosteroids at a dose of 1 to 2 mg/kg prednisone or equivalent once per day.
 
• When symptoms improve to Grade 1 or less, steroid taper should be started and continued over no less than 4 weeks.
 
• Permanently discontinue for inability to reduce corticosteroid dose to 10 mg or less of prednisone or equivalent per day within 12 weeks. Otherwise, Pembrolizumab treatment may be restarted and the dose modified as specified in the protocol
 

	Grade 3	
 
• Report overdose and liver toxicity ECIs within 24 hours
 
• Withhold Pembrolizumab
 
	
 
• Treat with systemic corticosteroids at a dose of 1 to 2 mg/kg prednisone or equivalent once per day.
 
• When symptoms improve to Grade 1 or less, steroid taper should be started and continued over no less than 4 weeks.
 
• Permanently discontinue for inability to reduce corticosteroid dose to 10 mg or less of prednisone or equivalent per day within 12 weeks. Otherwise, pembrolizumab treatment may be restarted and the dose modified as specified in the protocol
 

	Grade 4	

• Report overdose and liver toxicity ECIs within 24 hours

• Discontinue pembrolizumab

	

• Treat with systemic corticosteroids at a dose of 1 to 2 mg/kg prednisone or equivalent once per day.

--	---------	--	--

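### Table 10 merges Grade 3 and Grade 4 immune-related events into one withhold rule, which at Grade 4 contradicts the stop rules in Table 8, its note and Appendix 5

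*Combined protocol and SAP*

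**What the plan says.** Section 6.5 introduces Table 10 as guidance for irAEs that the protocol does not cover elsewhere. Its last row covers Grade 3 and Grade 4 together: "Withhold pembrolizumab Discontinue if unable to reduce corticosteroid dose to" below 10 mg prednisone equivalent a day within 12 weeks. A note adds that if an irAE has not returned to Grade 1 or lower within 12 weeks of the last administration, "study therapy discontinuation should be considered after discussion with" the manufacturer's clinical director.

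Three other rules cover the same residual events:

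- **Table 8 (Section 6.2.9.2)** ends with a catch-all row, "All Other Drug-Related Toxicity". Grade 3 or severe toxicity is held until it returns to Grade 0-1. Grade 4 is a permanent stop in both the restart column and the discontinuation column.
- **The note under Table 8** requires permanent discontinuation for any life-threatening event.
- **The Other block of Appendix 5** covers named events plus "Any additional Grade 3 or higher event which the physician considers to be immune related". Grade 3 is withheld, with a restart possible. Grade 4 is discontinued.

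Section 6.5, under other immune-related AEs, lists further reactions seen in a small share "of subjects treated with pembrolizumab: uveitis, myositis", Guillain-Barré syndrome, pancreatitis and severe skin reactions, with no action by grade. It also says: "Patients with symptomatic irECIs should immediately stop receiving pembrolizumab".

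**The concern.** Grade 4 is the grade at which the decision to re-expose a patient matters most, and four pieces of text bear on it. Three say stop. Table 10 says withhold, with a stop that depends only on the steroid taper. An investigator who opens Table 10, which is titled as the general approach to irAEs, meets a different instruction from one who opens Table 8 or Appendix 5. In a phase I trial whose primary objective is safety, dosing rules after a life-threatening event should read the same wherever they appear. What is at stake is consistent patient management. No estimate, error rate or escalation decision depends on it.

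**Working it through.** The plan states no figure to reproduce. The check sets the rules side by side and then asks whether Table 10's wording has support elsewhere.

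**Step 1. Residual events by grade.**

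| Source | Grade 3 | Grade 4 |
|---|---|---|
| Table 10 (Section 6.5) | Withhold; stop if the steroid taper fails | Same as Grade 3 |
| Table 8, residual row (Section 6.2.9.2) | Hold until Grade 0-1 | Permanent stop |
| Note under Table 8 | Stop on recurrence | Stop, as life-threatening |
| Appendix 5, Other | Withhold; restart possible | Stop |

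The note reaches Grade 4 through Appendix 4, item 5, which defines that grade as life-threatening. At Grade 3 the three residual rows agree on withholding. At Grade 4 Table 10 stands alone.

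**Step 2. Is a Grade 4 hold usual elsewhere?**

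- Table 8 has 10 rows. Seven stop at Grade 4: diarrhoea/colitis, liver tests, hyperthyroidism, infusion reaction, pneumonitis, renal, and all other. The remaining 10 − 7 = 3 are endocrine: type 1 diabetes/hyperglycaemia, hypophysitis and hypothyroidism.
- Appendix 5 has 13 event blocks, of which 3 are endocrine, leaving 13 − 3 = 10. Nine of those 10 stop at Grade 4: pneumonitis, haematologic, hepatic, neurologic, ocular, renal, two skin blocks, and other. The tenth, colitis, has a Grade 4 action cell that cannot be read in the text available. Table 8 and the colitis paragraph of Section 6.5 both stop it at Grade 4.

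Outside endocrine events, no readable entry in Table 8 or Appendix 5 supports a hold at Grade 4.

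**Step 3. Which events depend on the residual rows?** Section 6.5 lists five further irAEs. Four have a place in Appendix 5: uveitis (ocular), Guillain-Barré syndrome (neurologic), pancreatitis (named under Other) and severe skin reactions (skin blocks). Myositis has no named row in Table 8 or Appendix 5. It is still caught by the Table 8 residual row, the Table 8 note and the Appendix 5 catch-all. So 1 of 5 lacks a named row, but 0 of 5 lack a Grade 4 stop.

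**Step 4. The opening of Section 6.2.9.2.** This text says pembrolizumab is withheld for a list ending in "severe or life-threatening AEs as per Table 8 below", and it requires discontinuation on a "recurrence of the same severe or life-threatening event at the same grade or greater with re-challenge of pembrolizumab". That is looser than the table, but it defers to Table 8, where the residual Grade 4 action is a permanent stop. It does not rescue Table 10's wording.

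**The case against.** The strongest reply is that the protocol already resolves Grade 4. The note under Table 8 stops treatment for any life-threatening event. Table 10 is limited to irAEs not detailed elsewhere, and the Appendix 5 catch-all details every further immune-related event of Grade 3 or higher, so Table 10 yields at Grade 4. Section 6.5 also requires any irAE of Grade 2 or higher to be discussed at once with the Chief Investigator or delegate, and symptomatic irECIs to stop immediately. On this view the Grade 4 half of the row is redundant and reaches no patient.

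Most of this stands, and it is why the practical risk is small. It does not make the row correct. If Table 10 yields at Grade 4, the row prints an instruction that should never be followed; if it does not yield, it contradicts the other three rules. Nor does Table 10 keep to its stated scope: its Grade 2 row has a rule for recurrent pneumonitis, which is covered in Table 8, Table 11 and the pneumonitis paragraph of Section 6.5. Neither Section 6.2.9.2 nor Section 6.5 states a general order of precedence among the tables.

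Two stronger readings should be set aside. A reader might infer that Table 10 authorises re-dosing after a life-threatening irAE. It does not say so: it withholds, gives one condition for stopping, and is silent on restart. A reader might also infer that Grade 4 myositis has no governing stop rule because no row names it. The Table 8 note and both catch-all rows cover it.

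**Conclusion.** The inconsistency is real and confined to Grade 4: one row of Table 10 conflicts with the Table 8 residual row, the Table 8 note and the Appendix 5 residual block. It is a wording error between tables, not a choice about trial design, and it merits a minor safety-text correction. A DLT is defined by grade and relatedness in Section 3.2.1, so the DLT rules, the RP2D and the sample size do not change.

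This rests on two assumptions. The first is that the event is judged immune-related and drug-related, so that all the rules apply to it. The second is that the merged row is a drafting slip. The protocol does not say so, but the pattern in Table 8 and Appendix 5 points that way.

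The documents do not support using this point to justify a wider rewrite of the dose-modification rules. Adding endocrine exceptions to the Table 8 note, or ranking Appendix 5 above Table 8, would relax stop rules now in writing. Those are clinical decisions. A precedence rule between only those two tables would also miss a separate mismatch: Section 6.4.1.1 permanently stops Grade 3 enterocolitis, while Table 8 and the colitis paragraph of Section 6.5 hold Grade 3 colitis.

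**What to change.** Split the Table 10 row in two:

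- **Grade 3:** withhold pembrolizumab; discontinue if steroids cannot be reduced to 10 mg or less of prednisone equivalent a day within 12 weeks. This also replaces Table 10's threshold of under 10 mg with the one used in Table 8 and Appendix 5.
- **Grade 4:** permanently discontinue, except where Table 8, the endocrinopathies paragraphs of Section 6.5 or Appendix 5 give an event-specific endocrine rule. Grade 4 hyperthyroidism remains a permanent stop, as all three already require.

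The supportive-care column can stay as it is for both grades. The cost is one table row in the next amendment, with no change to visits, data collection or analysis.

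Three neighbouring matters should go to the sponsor's clinical team as separate questions: the looser opening wording of Section 6.2.9.2, the tension between the Table 8 note and that table's own endocrine rows, and the Grade 3 enterocolitis mismatch. None needs settling before the Table 10 row is corrected.

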#### *Immune-mediated pneumonitis*

Monitor subjects for signs and symptoms of pneumonitis. If pneumonitis is suspected, evaluate with radiographic imaging and exclude other causes. Administer corticosteroids for Grade 2 or greater events (initial dose of 1-2 mg/kg/day prednisone or equivalent followed by a taper), withhold pembrolizumab for moderate (Grade 2) pneumonitis, and permanently discontinue pembrolizumab for recurrent moderate (Grade 2), severe (Grade 3) or life-threatening (Grade 4) pneumonitis.

#### *Immune-mediated colitis*

Monitor subjects for signs and symptoms of colitis and exclude other causes of colitis. Administer corticosteroids for Grade 2 (if persists for >3 days) or greater events (initial dose of 1-2 mg/kg/day prednisone or equivalent followed by a taper), withhold pembrolizumab for moderate (Grade 2) or severe (Grade 3) colitis, and permanently discontinue pembrolizumab for life-threatening (Grade 4) colitis.

